6.1.1. Premedication

Subjects will receive the following premedications before all infusions with daratumumab:

- Dexamethasone (or equivalent in accordance with local standards) will be administered as described in Section 6.3.
- Paracetamol (acetaminophen) will be administered at a dose of 1 g PO 30 minutes to 2 hours before infusion.
- An antihistamine (clemastine 1 mg IV, cetirizine 10 mg PO, or equivalent) will be administered 30 minutes to 2 hours before infusion.

6.2. Lenalidomide

For Phase 1 and Phase 2, lenalidomide will be administered at a dose of 25 mg PO each day on Days 1 through 21 of each 28-day cycle. Cycle 1, Day 1 will be the day of the first full dose of daratumumab (Cycle 1 Visit 2). Lenalidomide will be administered until the subject experiences disease progression or unacceptable toxicity, whichever comes first.

On daratumumab infusion days, lenalidomide may be administered prior to or at the same time (preferred) as the premedications. A common side effect of lenalidomide is tiredness. On days when daratumumab is not administered, subjects may take their dose of lenalidomide in the evening.

6.2.1. Dose Adjustments of Lenalidomide

Dose adjustments of lenalidomide will follow the approved labeling as follows:

- Starting dose 25 mg
- Dose level 1 15 mg
- Dose level 2 10 mg
- Dose level 3 5 mg

Dose adjustments should be based on the highest grade of toxicity that is ascribed to lenalidomide.

6.2.1.1. Deep Vein Thrombosis and Pulmonary Embolism

Lenalidomide has been associated with DVT and PE. Therefore, all subjects should be prophylactically treated with aspirin at a dose of 100 to 150 mg PO daily. Subjects at increased risk of thromboembolic events (based on their medical history) should be treated with enoxaparin at a dose of 40 mg subcutaneously daily. The injection should be handled according to local practice.

6.2.1.2. Thrombocytopenia

If the subject's platelet count decreases, dose adjustments should be made according to the recommendations in Table 7.

Table 7: Lenalidomide Dose Adjustment for Thrombocytopenia

Platelet Count	Recommended Course of Action
• When count first falls to $< 30 \times 10^9 / L$	Interrupt lenalidomide treatment, follow complete
	blood count weekly
• When count returns to $\ge 30 \times 10^9 / L$	Resume lenalidomide at 15 mg
• For each subsequent drop in count to $< 30 \times 10^9 / L$	Interrupt lenalidomide treatment
• When count returns to $\ge 30 \times 10^9 / L$	Resume lenalidomide at the next lower dose level
	(10 mg or 5 mg) once daily. Do not decrease dose
	below 5 mg once daily

6.2.1.3. Neutropenia

If the subject experiences neutropenia, the investigator should consider the use of growth factors in the subject's management. If the neutrophil count decreases below $1.5 \times 10^9/L$ after the second cycle, the subject should be treated with G-CSF at a dose of 300 µg/day if his or her weight is less than 75 kg or 480 µg/day if his or her weight is 75 kg or more. G-CSF may be given daily or 2 to 3 times a week as appropriate to maintain the subject's neutrophil count above $1.0 \times 10^9/L$.

If the subject's neutrophil count decreases further, dose adjustments should be made according to the recommendations in Table 8.

Table 8: Lenalidomide Dose Adjustment for Neutropenia

Neutrophil Count	Recommended Course of Action
• When count first falls to $< 1.0 \times 10^9/L$	Interrupt lenalidomide treatment, start G-CSF treatment, follow complete blood count weekly
• When count returns to $\ge 1.0 \times 10^9/L$ and neutropenia is the only observed toxicity	Resume lenalidomide at 25 mg once daily
• When count returns to ≥ 1.0 × 10 ⁹ /L and other toxicity is observed	Resume lenalidomide at 15 mg once daily
• For each subsequent drop in count to $< 1.0 \times 10^9/L$	Interrupt lenalidomide treatment
• When count returns to $\ge 1.0 \times 10^9/L$	Resume lenalidomide at the next lower dose level
	(15, 10 mg, or 5 mg) once daily. Do not decrease
	dose below 5 mg once daily

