Bone marrow mononuclear cells from 4 patients with lenalidomide-refractory MM were incubated lenalidomide (3 μ M), daratumumab (10 μ g/mL), or in combination for 48 hours. Surviving MM cells were enumerated by Fluorescence-activated Cell Sorting analysis of CD138+ cells. The percentages of lysis of MM cells treated with lenalidomide, daratumumab, or lenalidomide + daratumumab were calculated as compared with the survival of MM cells treated with the control keyhole limpet hemocyanin antibody alone.

Finally, it was demonstrated that peripheral blood mononuclear cells isolated from patients during or just after lenalidomide treatment showed a significantly increased capacity to mediate daratumumab-dependent ADCC against multiple myeloma cells alone (van der Veer 2011).²⁹

Thus, in this ex vivo clinical setting, daratumumab-mediated multiple myeloma tumor cell killing was demonstrated to be significantly augmented by stimulating effector cells. In conclusion, preclinical data, both from the literature and the sponsor's own ex vivo studies, support the combination of daratumumab with an IMiD in the treatment of multiple myeloma.

Based on the current safety data from the ongoing GEN501 study (Section 1.1.5) and the safety information in the label for lenalidomide, the expected safety profile of daratumumab in this combination therapy study is considered manageable.

No major changes in thrombocyte counts over time have been observed during treatment with daratumumab in doses up to 4 mg/kg. Thrombocytopenia was an expected finding based on the data from preclinical studies. Because lenalidomide may cause thrombocytopenia, an additive effect cannot be excluded. Therefore, thrombocytopenia must be closely monitored, and dose adjustments in accordance with the label for lenalidomide must be followed during this study of the combination of daratumumab and lenalidomide. Lenalidomide also increases the risk of DVT and pulmonary embolism (PE). No thromboembolic events have been observed with daratumumab; however, a thrombocyte-sensitizing effect of daratumumab cannot be excluded. Therefore, aspirin should be administered to all subjects, and low-molecular weight heparin should be given to subjects who are at increased risk of thromboembolic events. Intense safety

monitoring by the sponsor and an Independent Data Monitoring Committee (IDMC) will be performed.

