6.2.1.4. Renal Impairment

Because lenalidomide is primarily excreted unchanged by the kidney, adjustments to the dose of lenalidomide are recommended to provide appropriate drug exposure in subjects with moderate or severe renal impairment. Lenalidomide dose adjustment should be instituted for subjects with a CrCl of 60 mL/minute or less. The recommended doses for subjects with multiple myeloma and renal impairment are shown in Table 9.

 Category
 Renal Function^a
 Dose

 Moderate renal impairment
 CrCl 30-60 mL/min
 10 mg every 24 hours

 Severe renal impairment
 CrCl < 30 mL/min (not requiring dialysis)	15 mg every 48 hours

 End-stage renal disease
 CrCl < 30 mL/min (requiring dialysis)	5 mg once daily. On dialysis days, administer the dose after dialysis

Table 9: Lenalidomide Dose Adjustment for Renal Impairment

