12.6.3. Pregnancy

Lenalidomide is an analog of thalidomide, which is a known human teratogen that causes life-threatening birth defects. Results of an embryo-fetal development study in nonhuman primates indicated that lenalidomide produced malformations in the offspring of female monkeys that received the drug during pregnancy. These malformations were similar to birth defects observed in humans after women were exposed to thalidomide during pregnancy. If lenalidomide is used during pregnancy, it may cause birth defects or death to a developing fetus. Women of childbearing potential must be advised to avoid pregnancy while receiving lenalidomide. Effective contraceptive methods should be used for 4 weeks before the first infusion of daratumumab, during therapy, during therapy interruptions, and for at least 6 months after completing therapy. The lenalidomide label warnings and advice must be followed throughout this study. See Exclusion Criterion #27 (Section 4.3) for definitions of effective, adequate methods of contraception.

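### The first-event restart rows in lenalidomide Tables 7 and 8 have no ceiling at the dose held, so a subject already at 10 or 5 mg would, on the printed row, restart at 15 mg or more

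*Protocol*

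**What the plan says.** Protocol Section 6.2.1 sets a descending ladder of 25, 15, 10 and 5 mg and introduces it with "Dose adjustments of lenalidomide will follow the approved labeling as follows".

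- **Table 7 (Section 6.2.1.2).** After the first platelet fall and recovery: "Resume lenalidomide at 15 mg".
- **Table 8 (Section 6.2.1.3).** After the first neutrophil fall and recovery: "Resume lenalidomide at 25 mg once daily" if neutropenia is the sole toxicity seen, and "Resume lenalidomide at 15 mg once daily" if there is other toxicity.
- **Later falls (both tables) and Section 6.2.1.5.** The restart is one level below the dose held; both tables set a 5 mg floor.
- **Table 9 (Section 6.2.1.4).** "Lenalidomide dose adjustment should be instituted for subjects with a CrCl of 60 mL/minute or less". Moderate impairment is dosed at "10 mg every 24 hours", and dialysis subjects receive 5 mg daily.

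Both cytopenia tables are headed as recommended courses of action. Two other places point to the label. Section 1.2, on thrombocytopenia, says "dose adjustments in accordance with the label for lenalidomide must be followed during this study of the combination of daratumumab and lenalidomide". Section 12.6.3, on pregnancy, says "The lenalidomide label warnings and advice must be followed throughout this study".

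**The concern.** The later-fall rows and Section 6.2.1.5 are relative to the dose held, but the first-event rows are absolute. They work for a subject on 25 mg. They do not mention a subject who reached 10 or 5 mg by another route before a first event under that table. For such a subject the printed row raises lenalidomide immediately after a cytopenia that required interruption.

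The rules remain in force. Attachment 9 continues dosing on the established regimen under Amendment 8. Meanwhile laboratory checks are local (Section 9.2.2), the data monitoring committee no longer reviews safety data (Section 11.13), and on-site monitoring visits are usually at least 24 weeks apart (Section 17.8). With less central oversight, sites rely more on the written rule. What is at stake is individual subject safety, not an estimate or an error rate.

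**Working it through.** The plan gives no figure to reproduce; the check applies the printed rows to each dose a subject could hold.

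**Step 1. Dose held against restart dose (mg), as printed.**

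| Held | Table 7, first | Table 8, first, neutropenia alone | Table 8, first, other toxicity | Later falls (either table) |
|---|---|---|---|---|
| 25 | 15 | 25 | 15 | 15 |
| 15 | 15 | 25 | 15 | 10 |
| 10 | 15 | 25 | 15 | 5 |
| 5 | 15 | 25 | 15 | 5 |

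From 10 or 5 mg, all three first-event columns go up. The later-fall column never does. Table 7 prints 15 mg without a frequency; it is taken here as once daily.

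**Step 2. Size of the rise to 15 mg.**

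- From 10 mg: 15/10 = 1.5-fold. Over 21 dosing days, 10 × 21 = 210 mg becomes 15 × 21 = 315 mg.
- From 5 mg: 15/5 = 3-fold. Over 21 days, 5 × 21 = 105 mg becomes 315 mg.

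**Step 3. How a subject gets there by toxicity.** Let P be a platelet fall, N a neutrophil fall and O another Grade 3 or 4 toxicity under Section 6.2.1.5. Start at 25 mg and apply the rows as printed. Count any earlier P or O as *observed* toxicity, so that a first N after one resumes at 15 mg and a first N with none resumes at 25 mg.

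- One event: 0 of 3 orderings give a rise.
- Two events: 0 of 3 × 3 = 9.
- Three events: only PP, PO and OO leave the subject at 10 mg after two events. The orderings that then meet an unused first-event row are PPN, PON, OOP and OON, which is 4 of 3 × 3 × 3 = 27. Each runs 25 → 15 → 10 → 15 mg.
- Four events: PPPN and OOOP run 25 → 15 → 10 → 5 → 15 mg. NNNP runs 25 → 25 → 15 → 10 → 15 mg.

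If other toxicity accompanies the first neutropenia, N, N, P runs 25 → 15 → 10 → 15 mg, again three events. These are counts of orderings, not probabilities.

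**Step 4. The narrow reading.** If an earlier toxicity that has resolved is not counted as *observed*, a first N always resumes at 25 mg. A rise then appears at two events: PN and ON both go 25 → 15 → 25 mg, and 25/15 = 1.67-fold.

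**Step 5. With a ceiling.** Set restart = min(printed dose, dose held). From 15, 10 and 5 mg, every first-event row then restarts at 15, 10 and 5 mg. From 25 mg the results are 15, 25 and 15 mg, unchanged from Step 1. No restart exceeds the dose held.

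**The case against.** The strongest reply is that the tables are recommendations within a section on dose adjustment, built on a descending ladder. Table 7's later-fall row offers only 10 or 5 mg, so its first row plainly describes a subject leaving 25 mg. Most investigators would not raise the dose of a subject already reduced. This stands as a limit on weight. A reader might infer that the protocol requires escalation after toxicity; it does not. But an investigator who caps the dose departs from the printed row, and no other text supplies the cap.

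Second, the label governs and may deal with combined reductions. That cannot be settled from these documents. Section 6.2.1 presents the tables as what the labeling says, so sites will work from them; the gap shown is in the protocol's own text.

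Third, a reader might add the renal route and its larger multiples: 25/10 = 2.5-fold, 25/5 = 5-fold, or a doubling from 15 mg every 48 hours (7.5 mg/day) to 15 mg daily. These require setting aside Section 6.2.1.4, which is a standing rule for as long as CrCl is 60 mL/min or less. Its reason, renal excretion, does not lapse when counts recover. Entry also excludes CrCl at or below 60 mL/min (Section 4.3, criterion 15), so the route needs on-study decline. What survives is that no sentence says which table governs.

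Fourth, a reader might cite Section 3.2.3.2, where neutropenia made up most Grade 3 events in Phase 1, as evidence that the sequence is common. It gives no timing. Early neutropenia would use up Table 8's first-event row before other reductions occurred.

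Finally, exposure is small. Section 9.2 says every subject has had at least 24 months of study drug or has stopped. No document shows that an affected subject exists.

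**Conclusion.** The gap is real on the printed text, and minor. A subject held at 10 or 5 mg after reductions for toxicity would, on the printed first-event row, restart at 15 mg or more: at least 1.5-fold from 10 mg and 3-fold from 5 mg. If earlier toxicity counts as *observed*, at least three dose-modifying events are needed, and the three-event rises are all 10 to 15 mg. Larger toxicity-route rises need a fourth event or the narrow reading. For renal reductions the defect is only that precedence is unstated.

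This rests on applying the rows as written and on the protocol text alone. Confidence is medium because the label is not available. The number of affected subjects is unknown and likely very small. A reader might infer an effect on the adverse event incidence that forms the primary endpoint; nothing in the documents supports one.

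**What to change.** Add to the first-event rows of Tables 7 and 8: *or at the dose held at interruption, if lower*. State in Section 6.2.1.4 that the Table 9 dose remains the upper limit while CrCl is 60 mL/min or less. Check both against the lenalidomide label before issue.

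Add no discretion to restart a level below the dose held: it would let a 25 mg subject with isolated first neutropenia drop to 15 mg, where Table 8 says 25 mg. Subjects at 25 mg and the later-fall rows are then unaffected.

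The cost is a short wording change (by amendment, under Section 17.1), a label check and a site memo, with no new data or visits. The downside is that a subject whose earlier reason for reduction has resolved stays on the lower dose unless another rule raises it.

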6.2.1.4. Renal Impairment

Because lenalidomide is primarily excreted unchanged by the kidney, adjustments to the dose of lenalidomide are recommended to provide appropriate drug exposure in subjects with moderate or severe renal impairment. Lenalidomide dose adjustment should be instituted for subjects with a CrCl of 60 mL/minute or less. The recommended doses for subjects with multiple myeloma and renal impairment are shown in Table 9.

 Category
 Renal Function^a
 Dose

 Moderate renal impairment
 CrCl 30-60 mL/min
 10 mg every 24 hours

 Severe renal impairment
 CrCl < 30 mL/min (not requiring dialysis)	15 mg every 48 hours

 End-stage renal disease
 CrCl < 30 mL/min (requiring dialysis)	5 mg once daily. On dialysis days, administer the dose after dialysis

Table 9: Lenalidomide Dose Adjustment for Renal Impairment

6.2.1.5. Other Grade 3 or 4 Adverse Events

For other Grade 3 or 4 toxicities judged by the investigator to be related to lenalidomide alone, treatment with lenalidomide should be interrupted and restarted at the next lower dose level once the toxicity has resolved to Grade 2 or less. Treatment with daratumumab and dexamethasone may continue.

6.3. Dexamethasone

For Phase 1 and Phase 2, dexamethasone (or equivalent in accordance with local standards; see Attachment 4 for conversion table) will be administered at a total dose of 40 mg weekly. As of Amendment 5, subjects older than 75 years or underweight (body mass index [BMI] <18.5), the dexamethasone dose may be administered at a dose of 20 mg weekly. On weeks when daratumumab is administered the 20 mg dose should be administered as the pre-medication per protocol. During weeks when the subject receives an infusion of daratumumab, dexamethasone will be administered on infusion days at a dose of 20 mg IV before the infusion and 20 mg PO the day after the infusion. During weeks when no daratumumab infusion is administered, dexamethasone will be administered at a dose of 40 mg/week PO. Dexamethasone will be administered until the subject experiences disease progression or unacceptable toxicity, whichever comes first.

After Cycle 6, the dose of dexamethasone may be reduced at the investigator's discretion. The 20-mg IV dose of dexamethasone given before the infusion on the day of daratumumab infusions must not be decreased. When dexamethasone is reduced to 20 mg/week and is given as preinfusion medication, subjects may receive low-dose methylprednisolone (≤20 mg) PO (or equivalent in accordance with local standards), for the prevention of delayed infusion-reaction reactions as clinically indicated.

6.3.1. Dose adjustments of Dexamethasone

Investigators should refer to the manufacturer's full prescribing information for side effects associated with dexamethasone. Dexamethasone administration may be held for up to 2 weeks until the toxicity resolves to Grade 1 or baseline levels.

6.4. Delaying or Skipping Treatment

After completion of each cycle, initiation of a new cycle should be delayed for at least 1 week if the subject experiences toxicity. A subject whose cycle is delayed should be evaluated weekly for resolution or recovery of the toxicity, and a decision regarding further delay or initiation of

Key: CrCl = creatinine clearance.

Estimated by CrCl as calculated by the Cockcroft-Gault, Diet in Renal Disease (MDRD), or Chronic Kidney Disease Epidemiology Collaboration (CKD-EPI) formulas formula (Attachment 7).

the next cycle should be made. However, the start of a new cycle after more than a 3-week delay (with all study therapy withheld) may occur only if there is clear clinical benefit and only after approval by the sponsor.

Refer to Section 6.6.1 for details on management of infusion-related reactions. **ONLY if any of the following criteria below are met, and the event cannot be ascribed to lenalidomide, the daratumumab infusion must be held to allow for recovery from toxicity**. The following parameters must be met on the first day of a new cycle (after Cycle 1):

- Platelet count $\geq 50 \times 10^9/L$
- Febrile neutropenia of any grade
- Neutropenia with infection, of any grade
- Hemoglobin $\geq 8.0 \text{ g/dL}$ ($\geq 4.96 \text{ mmol/L}$) (prior red blood cell transfusion or recombinant human erythropoietin use is allowed)
- ANC $\ge 0.75 \times 10^9 / L$
- Nonhematologic toxicity of Grade 3 or higher must have recovered to baseline or Grade 1 or less unless otherwise specified

A subject whose cycle is delayed should be evaluated at least weekly for resolution of the toxicity. For severe hematologic toxicity (Grade 3 or higher), a complete blood count may be repeated more frequently as necessary until the requirements for reinitiating treatment are met.

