6. DOSAGE AND ADMINISTRATION

The start of a cycle is defined as the start of any of the study treatments (ie, daratumumab or Len/Dex). If all treatments are held, then it should be reported as a cycle delay.

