As per Amendment 8, subjects will continue to be dosed as per the Amendment 7 schedule (1 cycle is 28 days) and Table 4.

Data collection will be limited to SAEs and SPMs, see details in Section 12 and Attachment 9.

Daratumumab will be provided by the sponsor until it is approved for use in combination with lenalidomide and dexamethasone for patients with relapsed refractory multiple myeloma and is commercially available or can be accessed from another source. Subjects receiving treatment will be transitioned from study drug to commercial product once commercial product is available in their region (or when daratumumab can be accessed from another source). In these circumstances, the sponsor and investigator will support transition of the subject to ensure that treatment continues and remains uninterrupted. Subjects who are unable to switch to commercial supplies will continue to remain in the study. All subjects will be followed for 3 years after the last dose of lenalidomide, to enable collection of SPMs.

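### Protocol Section 6.4 gives two conflicting rules for a low Day 1 count ascribed to lenalidomide, so the text supports both infusing daratumumab and not starting the cycle

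*Protocol*

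**What the plan says.** Section 6.4 contains three instructions.

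- **Opening rule.** After each completed cycle, "initiation of a new cycle should be delayed for at least 1 week if the subject experiences toxicity". It gives no grade and no test of which drug caused the toxicity.
- **Hold sentence (bold).** "ONLY if any of the following criteria below are met, and the event cannot be ascribed to lenalidomide, the daratumumab infusion must be held".
- **Day 1 sentence.** It follows directly: "The following parameters must be met on the first day of a new cycle (after Cycle 1"). It has no lenalidomide clause and does not say which treatment is stopped if a parameter fails.

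One list serves the last two sentences: platelets >=50 x 10^9/L; febrile neutropenia; neutropenia with infection; hemoglobin >=8.0 g/dL; ANC >=0.75 x 10^9/L; and recovery of nonhematologic toxicity of Grade 3 or higher, with an allowance for exceptions stated elsewhere.

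Related text:

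- Section 6: "The start of a cycle is defined as the start of any of the study treatments (ie, daratumumab or Len/Dex"). Only when all treatments are held is a cycle delay reported.
- Section 6.2.1.2, if the "platelet count decreases, dose adjustments should be made according to the recommendations in Table 7". Table 7 interrupts lenalidomide below 30 x 10^9/L.
- Section 6.2.1.3, if the "neutrophil count decreases further, dose adjustments should be made according to the recommendations in Table 8". Table 8 interrupts lenalidomide below 1.0 x 10^9/L.
- Section 6.2.1.5, for other Grade 3 or 4 toxicity judged related to lenalidomide alone: lenalidomide is interrupted, and "Treatment with daratumumab and dexamethasone may continue".
- Section 9.1.3.1, under Amendment 8: "subjects will continue to be dosed as per the Amendment 7 schedule (1 cycle is 28 days").

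**The concern.** In the hold sentence, a criterion being met triggers a hold. In the Day 1 sentence, a parameter being met permits a start. Four items are conditions to satisfy and two are adverse events. Read literally, the hold sentence would stop daratumumab for an adequate platelet count, and the Day 1 sentence would require febrile neutropenia to be present. A reader can guess the direction: hold if a minimum is missed or an event is present. That guess does not settle whether attribution to lenalidomide matters on Day 1.

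This is a mandatory toxicity rule, and the situation is foreseeable. Section 3.2.3.2 says that most Grade 3 events in Phase 1 were neutropenia attributed to lenalidomide, and Section 1.2 says that lenalidomide may cause thrombocytopenia. What is at stake is mainly the safety of subjects still on treatment.

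Divergent practice would also be hard to see now. Laboratory tests are local (Section 9.2.2), data collection is limited to SAEs and SPMs (Section 9.2), on-site monitoring visits are usually at least 24 weeks apart (Section 17.8), and the IDMC stopped reviewing safety after the primary analysis (Section 11.13).

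**Working it through.** The plan gives no figure to reproduce. The check applies each rule to one situation: a Day 1 value, after Cycle 1, that is ascribed to lenalidomide. Counts are x 10^9/L.

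| Day 1 value | Lenalidomide | Hold sentence on daratumumab | Day 1 sentence |
|---|---|---|---|
| Platelets 30 to <50 | Table 7: no interruption | No hold required | Not met |
| Platelets <30 | Table 7: interrupt | No hold required | Not met |
| ANC 0.75 to <1.0 | Table 8: interrupt | No hold required | Met |
| ANC <0.75 | Table 8: interrupt | No hold required | Not met |
| Hemoglobin <8.0 g/dL | No table; Section 6.2.1.5 if Grade 3 or 4 and related to lenalidomide alone | No hold required | Not met |

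Four of the five rows conflict. ANC of 0.75 to <1.0 does not, because the Day 1 minimum is satisfied.

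**Items affected.** Platelets, hemoglobin and ANC have a numeric minimum and no allowance for exceptions, which makes 3 of 6. The nonhematologic item has that allowance, so Section 6.2.1.5 may be its exception.

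**Could the two sentences govern different things?** Suppose the Day 1 sentence stops the cycle and the hold sentence stops daratumumab. Under Section 6, giving daratumumab starts the cycle, so it cannot be both allowed and part of a cycle that must not start. Len/Dex alone also starts a cycle, so the Day 1 sentence does not say which drug is meant.

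**Could they apply on different days?** The text does not say so. From Cycle 7, daratumumab is given only on Day 1 (Section 6.1). Cycle 7 follows 6 x 28 = 168 days of undelayed treatment. Subjects continuing under Amendment 8 have had at least 24 months of daratumumab (Attachment 9), which is 24 x 365.25/12 = 730.5 days by the SAP's definition of a month (Section 2.6.5). On this schedule their infusions are Day 1 infusions, and both sentences apply to each one.

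**Knock-on effect.** The reading chosen decides whether a cycle delay is reported (Section 6). It can also decide whether the limit of more than 3 weeks, after which sponsor approval is needed, comes into play (Sections 6.4, 10.1 and 10.2). The Cycle 2 Day 1 DLT item is not triggered by a count due solely to lenalidomide, because it covers only toxicity related to daratumumab (Section 6.5).

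**The case against.** The best counter-reading is that the bold hold sentence alone governs daratumumab, and that the next sentence, which states no consequence, only introduces the list and its timing. Other text fits this. Section 6.2.1 adjusts lenalidomide by toxicity ascribed to it, Section 6.2.1.5 lets daratumumab continue when lenalidomide alone is responsible, and Section 9.1.3 lets the other components continue when one is stopped.

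The reading is coherent, but the text does not establish it. The Day 1 sentence is worded as an obligation. Section 6.4 closes by having blood counts repeated until the conditions for restarting are satisfied, which treats the list as start requirements without regard to cause. Section 6.2.1.5 covers events other than those in the platelet and neutrophil sections.

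Several narrower points stand:

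- The opening rule is advisory and leaves further delay to a decision, so it adds less weight than the two mandatory sentences.
- The change log for Amendment 6 describes the two neutropenia items as reasons for dose delay, so the intended direction of the list can be inferred.
- Hemoglobin has some attribution guidance through Section 6.2.1.5, and Tables 7 and 8 settle lenalidomide for the lowest counts. Platelets of 30 to <50 x 10^9/L are the clearest gap.
- A rule on when a hold is compulsory does not clearly forbid an investigator from holding for safety, and harm has not been shown.
- The number of subjects still treated and the frequency of such counts are unknown.

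**Conclusion.** The concern holds. Section 6.4 contradicts itself on a mandatory safety rule, and its list fits neither lead-in as written. The open conflict covers 3 of 6 items and is sharpest for platelets of 30 to <50 x 10^9/L, where one sentence requires no daratumumab hold, the other says the start condition fails, and Table 7 leaves lenalidomide running.

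This rests on the current text and on the value being ascribed to lenalidomide; it does not depend on how often that happens. No sample size, power or collected data would change. It should be fixed because dosing continues under Amendment 8. No view is taken on which clinical rule is right.

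**What to change.** Reconcile the passages. Split the list into conditions for starting a cycle and events that require a daratumumab hold, each with one lead-in and one direction. For each part, state:

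- whether the lenalidomide qualifier applies;
- whether daratumumab alone or the whole cycle is affected;
- how the rule relates to the opening delay rule, Tables 7 and 8, and Section 6.2.1.5.

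The clinical content is for the sponsor's clinical team.

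The cost is a wording clarification and a letter to sites, with no new data or procedures. Section 17.1 requires a formal amendment for any protocol change, with prior IEC/IRB approval unless the change is purely logistic or administrative. A toxicity rule is unlikely to qualify for that exception, so time for approval should be allowed.
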